5.2.3. Analyses for Proportions based on Number of Successes

Endpoints defined as the number of successes out of a possible number of tests for each participant at each timepoint will be analyzed using a generalized mixed model assuming a Binomial distribution with a logit link. For example, for the number of skills gained in the NSAA, the endpoint is the number of skills gained out of the number of skills that can be gained (score 0 at Baseline). The maximum likelihood estimation method with Newton Raphson iteration will be used. The fixed effect of treatment group (as a categorical variable) will be included in the model along with any covariates given in [Section 6](#). The effect of

treatment will be examined using the Wald chi-square statistic (CHISQ option). LS means and 95% CIs and the difference in LS means and 95% CIs will be estimated using the z-statistic, by defining degrees of freedom to be infinite in the model (DDFM=NONE). The inverse link transform (ILINK) will be applied to obtain the LS means on the original scale, which will represent average proportions of success.

The estimate of difference in LS means when back-transformed will represent an odds ratio comparing the odds of a success occurring between two treatment groups. In order to represent these proportions as meaningful counts of success, the proportions will be multiplied by the average of the baseline values of the number of tests across all participants, irrespective of treatment group. For example, for number of skills gained, the average baseline number of skills that can be gained will be calculated. Then the back-transformed LS means representing the proportion of successes for each treatment group will be multiplied by this average baseline value, to give a representation of the average number of skills gained for each treatment group, for the population in this study.

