6.2.3.1. Main Analysis

- Estimand strategy: Secondary Estimand ([Section 2.2.2](#)).
- Analysis set: FAS ([Section 4](#)).
- Analysis methodology: For each participant, the number of skills gained at Week 52 will be expressed as a proportion of the number of skills at Baseline that could be gained (numerator is the number of items on NSAA gained at Week 52 and denominator is number of items on NSAA with score 0 at baseline). The number of skills either improved or maintained at Week 52 will be expressed as a proportion of the number of items at Baseline that could be improved or maintained (numerator is the number of items on NSAA improved or maintained at Week 52 and denominator is number of items on NSAA which is 17). These proportions will be analyzed using a generalized mixed linear model with a Binomial distribution and logit link ([Section 5.2.3](#)) including terms for treatment group and Screening age covariate (continuous variable).
- Intercurrent events and missing data: All available data at Week 52 will be included. The intercurrent events and missing data will be handled as described in [Section 2.2.2](#).
- The number (%) of participants with 0, 1, 2, 3, etc. with skills gained and the number (%) of participants with 0, 1, 2, 3, etc. with skills improved/maintained as observed at Week 52 will be provided for fordadistrogene movaparvovec and placebo. The count of skills gained at Week 52 and count of skills either improved or maintained at Week

52 will be summarized by treatment group using descriptive statistics (including, N, mean, SD, median, Q1, Q3, minimum, and maximum).

Additionally, for the endpoint, number of skills gained, the number of skills that could be gained at Baseline (those with value 0 at Baseline) will be summarized for each treatment group and overall by descriptive statistics (including, N, mean, SD, median, Q1, Q3, minimum, and maximum).

- The fordadistrogene movaparvovec and placebo back-transformed LS means (ie, mean proportion of skills) and 95% CIs along with the back-transformed difference between the LS means (ie, ratio of mean proportions of skills) and 95% CI at Week 52 will be provided. Two-sided p-value will also be provided.

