- An estimate of the mean number of skills gained at Week 52, based on the analysis model, can be derived by multiplying the proportion of skills gained (the back-transformed LS Mean) for each treatment group by the mean number of skills at Baseline that could be gained across all participants, irrespective of treatment group.

An estimate of the mean number of skills improved or maintained at Week 52, based on the analysis model, can be derived by multiplying the proportion of skills improved or maintained (the back-transformed LS Mean) for each treatment group by 17, which is the number of skills at Baseline that could be improved or maintained.

Graphical displays:

- The number (%) of participants with 0, 1, 2, 3, etc. skills gained at Week 52 will be displayed graphically in a bar chart with a bar for each treatment arm. Similarly, the number (%) of participants with 0, 1, 2, 3, etc. skills improved/maintained at Week 52 will be displayed graphically in a bar chart with a bar for each treatment arm.

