Appendix 5.3. Sample SAS Code for the Number of Skills Gained at Week 52 Analysis

```
/*save overall baseline mean as variable base_mean*/

proc sql;

  select avg(denomi) into: base_mean

  from adrs2 where ^missing(TRT01P);

Quit;

%put &base_mean;

proc glimmix data=adrs2;

  class TRT01P;

  model prop_skills = TRT01P agemodel / dist=bin link=logit chisq ddfm=NONE;

  lsmeans TRT01P / cl ilink ;

  lsmeans TRT01P / at agemodel=4 cl ilink ;

  lsmeans TRT01P / at agemodel=5 cl ilink ;
```

```

lsmeans TRT01P / at agetmodel=6 cl ilink ;
lsmeans TRT01P / at agetmodel=7 cl ilink ;
estimate 'Treat diff' TRT01P 1 -1 / cl ilink;
ods output LSMMeans=means4 estimates=est4;

run;

```

```

Data means5;

set means4 ;

extimate _MU_Gained=(MU)*&base_mean;

if agetmodel ^in (4, 5, 6, 7) & ^missing(TRT01P);

run;

```

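### Number of skills gained: Section 5.2.3 describes successes out of gainable skills, but the Appendix 5.3 code fits one unweighted proportion per boy, which changes the derived count, odds ratio, SE and p-value

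*SAP*

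**What the plan says.** SAP Section 5.2.3 sets out the method for endpoints that count successes out of a number of tests. Its own example is this endpoint: "the endpoint is the number of skills gained out of the number of skills that can be gained (score 0 at Baseline"). The model is binomial with a logit link. To return to a count, "the proportions will be multiplied by the average of the baseline values of the number of tests across all participants, irrespective of treatment group".

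Section 6.2.3.1 expresses each boy's result as a proportion whose "denominator is number of items on NSAA with score 0 at baseline", and says that it is the proportions that are analysed. The denominator therefore differs between boys. The mean count per arm is then obtained as follows: "multiplying the proportion of skills gained (the back-transformed LS Mean) for each treatment group by the mean number of skills at Baseline" (here, the gainable items). For skills improved or maintained, the denominator is 17 for every boy.

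Appendix 5.3 gives the only code for the endpoint. The multiplier comes from "select avg(denomi) into: base_mean", over all records with a treatment value. The model line is "model prop_skills = TRT01P agemodel / dist=bin link=logit chisq ddfm=NONE", and the count is formed by "extimate _MU_Gained=(MU)*&base_mean;". There is no trials variable and no weight statement.

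Section 5.1 places number of skills gained fourth and last in the fixed sequence of alpha-controlled secondary endpoints. Number improved or maintained is third.

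**The concern.** The text and the code describe two different analyses. In a successes-out-of-trials model, a boy with six gainable items carries six times the information of a boy with one. In the code as written, each boy is one trial whatever his denominator.

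This has two consequences. First, the back-transformed proportion becomes an average over boys rather than over gainable items, and its product with the mean denominator need no longer be the mean count. Second, and more important, the same model line produces the odds ratio, its confidence interval and the p-value for an endpoint under type I error control. Those results would not come from the model that Section 5.2.3 describes.

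**Working it through.** The SAP states no figure for skills gained, so there is none to reproduce. Notation: n is a boy's number of items scored 0 at Baseline, y is the number gained at Week 52, and p = y/n.

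**1. Identity.** mean(y) = mean(p) × mean(n) + cov(p, n). A product built on equally weighted boys omits the covariance. A product built on the pooled proportion does not, since [sum(y)/sum(n)] × mean(n) = mean(y).

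**2. Two-boy illustration.** One boy gains 1 of 1 and the other gains 1 of 6.
- Mean count: (1 + 1)/2 = 1.0
- Equal weight per boy: (1 + 1/6)/2 = 0.583; × 3.5 = 2.04
- Pooled: 2/7 = 0.286; × 3.5 = 1.0

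**3. Simulated trials.** 99 boys, 2:1, 300 replicates, binomial-logit with treatment and age. The distributions of n, the treatment log odds ratio of 0.5 and the slopes (change in log-odds of gaining a skill per extra 0-item) are all assumptions, because the SAP gives none. Cells show active/placebo.

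| n | Slope | Mean count | Events/trials × mean n | As coded × mean n | Active-arm error as coded |
|---|---|---|---|---|---|
| Uniform 1–6, mean 3.5 | -0.4 | 1.400/1.026 | 1.400/1.030 | 1.667/1.272 | +19% |
| | -0.2 | 1.522/1.121 | 1.521/1.122 | 1.661/1.246 | +9% |
| | 0 | 1.654/1.240 | 1.651/1.241 | 1.649/1.234 | about 0 |
| | +0.2 | 1.804/1.382 | 1.802/1.379 | 1.659/1.240 | -8% |
| Skewed, mean 2.84, some zeros | -0.4 | 0.860/0.615 | 0.865/0.623 | 1.222/0.921 | +42% |
| | -0.2 | 1.042/0.746 | 1.046/0.748 | 1.259/0.925 | +21% |
| | 0 | 1.338/0.992 | 1.338/0.987 | 1.333/0.980 | about 0 |
| | +0.2 | 1.664/1.325 | 1.660/1.311 | 1.436/1.083 | -14% |

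Events/trials stays within about 1% of the mean count in every row. The coded version does so only at slope 0.

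**4. Standard error.** With p common, a boy contributes information n·p(1-p) under events/trials and p(1-p) as coded. The SE ratio is then roughly the square root of mean n: √3.5 = 1.87. An emulation with n uniform 1–6 and a log odds ratio of 0.5 gave a treatment SE of about 0.24 under events/trials and 0.45 as coded (0.24 × 1.87 = 0.449). Rejection at two-sided 0.05 fell from 44–57% to 4–9% across four slopes.

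**5. Improved or maintained.** With n = 17 for every boy, cov(p, n) = 0, so the proportion and count are not biased by the weighting (check: 11.8 by both routes). If the same code template were used there, the SE would be inflated by about √17 = 4.1.

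**The case against.** Several counter-arguments are good, and they limit the point.

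- **The product of a proportion and a mean denominator is not itself an error.** A reader might infer that Sections 5.2.3 and 6.2.3.1 must drop it. Step 3 shows otherwise: under the model Section 5.2.3 describes, it recovers the mean count whatever the relation between share and denominator.
- **The derived count is not a headline result.** The SAP offers it as an estimate that can be derived and as a representation on the count scale. The test does not use the multiplication, and observed counts are tabulated by arm.
- **The arm difference does not carry the same error.** A reader might infer that it is scaled alike. The error in each arm is additive and partly cancels. In the first row the arms are off by +19% and +24%, but the difference is 0.395 against 0.374 (+6%). In the worst row the arms are off by +42% and +50%, and the difference is 0.301 against 0.245 (+23%). The SAP plans no arm difference in counts; the planned contrast is on the odds scale.
- **A gap from the raw arm mean is not in itself a fault,** since the figure is age-adjusted and uses a pooled denominator by design.
- **The code is labelled sample code.** This carries less weight. It is the only code given for the endpoint, and Section 6.2.3.1 speaks of analysing proportions, so the text does not clearly overrule it.

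None of these answers the effect on the odds ratio, SE and p-value.

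**Conclusion.** The point holds as a mismatch between Section 5.2.3 and Appendix 5.3. Run as coded, the derived mean count is off by roughly the covariance of share gained and number of 0-items. Its direction and size are unknown in advance, and it is zero if the two are unrelated; the assumed scenarios gave +42% to -14% in the active arm. The inferential results for an alpha-controlled endpoint would not be those of the stated model, with an SE nearly twice as large under the assumed inputs. Being last in the sequence, this endpoint gates no other. If the template were reused for improved or maintained, the inflated SE there would also affect whether skills gained is formally tested.

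The conclusion assumes one record per boy, as the per-participant proportion in Section 6.2.3.1 implies. It also takes a single response with no trials or weight to mean one trial per boy; this was emulated in Python and not run in SAS. The larger SE should not be read as a deliberate allowance for correlation between a boy's items: the SAP describes none here, and the SE of the events/trials model under such correlation is a separate question.

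**What to change.** 1. In Appendix 5.3, replace the single response with `gained/denomi` in events/trials form, or weight by `denomi`. Use the same form, with 17 as the trials, if the template serves the improved/maintained endpoint.
2. In Section 6.2.3.1, reword the sentence on analysing proportions so that it matches the successes-out-of-trials description in Section 5.2.3.
3. State that `avg(denomi)` is taken over the same FAS boys to whom the count applies. Boys with no 0-item have no proportion to model but may enter the mean; say whether they are included, contributing a count of zero, or excluded from both the mean and the count.

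The product with the mean denominator in Sections 5.2.3 and 6.2.3.1 can then stay. Standardising over individual boys is optional. The cost is a line or two of code and some SAP wording, with no new data.

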6.2.3.2. Sensitivity Analysis

This analysis is the same as the main analysis in [Section 6.2.3.1](#) except data from the rater from Clinical Site 1024 with potential data quality issues will be excluded from the analysis.

6.2.4. Rise from Floor and 10 Meter Run/Walk Test

Endpoints:

- Change from Baseline at Week 52 in the 10 meter run/walk test velocity.
- Change from Baseline at Week 52 in the rise from floor velocity.

6.2.4.1. Main Analysis

- Estimand strategy: Secondary Estimand ([Section 2.2.2](#)).
- Analysis set: FAS ([Section 4](#)).

- Analysis methodology: Change from baseline in velocity will be analyzed using an MMRM approach ([Section 5.2.1.1](#)) including visits through Week 52 where NSAA is assessed (ie, Weeks 9, 18, 35, 52) with additional fixed effects for Baseline velocity (continuous variable), Screening age covariate (continuous variable), Baseline by visit interaction, and Screening age covariate by visit interaction.
- Intercurrent events and missing data: All available data in the reporting period will be included. The intercurrent events and missing data will be handled as described in [Section 2.2.2](#)
- N, mean, SD, median, Q1, Q3, minimum, and maximum at Baseline and all visits through Week 52 where NSAA is assessed for observed velocities of the endpoints and changes from baseline in velocity will be provided for fordadistrogene movaparvovec and placebo.
- The fordadistrogene movaparvovec and placebo LS means, standard error of each LS mean, and 95% CIs for the LS means along with the difference between the LS means (fordadistrogene movaparvovec minus placebo) and the corresponding standard error, two-sided p-value, and 95% CI will be provided for change from baseline for all visits through Week 52 where NSAA is assessed.

Graphical displays:

- The fordadistrogene movaparvovec and placebo LS means, and 95% CIs for the LS means for each visit will be displayed graphically.

6.2.4.2. Sensitivity Analysis

- This analysis is the same as the main analysis in [Section 6.2.4.1](#) except data from the rater from Clinical Site 1024 with potential data quality issues will be excluded from the analysis.

6.2.5. PODCI Subscales

6.2.5.1. Main Analysis

Endpoints:

- Change from Baseline at Week 52 in the Modified PODCI: Transfer and Basic Mobility Core Scale (Pediatric Parent)
- Change from Baseline at Week 52 in the Modified PODCI: Sports and Physical Functioning Core Scale (Pediatric Parent)

Analysis:

- Estimand strategy: Secondary Estimand ([Section 2.2.2](#)).

- Analysis set: FAS ([Section 4](#)).
- Analysis methodology: Change from baseline will be analyzed using an MMRM approach ([Section 5.2.1.1](#)) including visits through Week 52 where PODCI is assessed (ie, Weeks 35 and 52) with additional fixed effects for Baseline (continuous variable), Screening age covariate (continuous variable), Baseline by visit interaction, and Screening age covariate by visit interaction.
- Intercurrent events and missing data: All available data in the reporting period will be included. The intercurrent events and missing data will be handled as described in [Section 2.2.2](#)
- N, mean, SD, median, Q1, Q3, minimum, and maximum at Baseline and all visits through Week 52 where PODCI is assessed for observed values and changes from baseline will be provided for fordadistrogene movaparvovec and placebo.
- The fordadistrogene movaparvovec and placebo LS means, standard error of each LS mean, and 95% CIs for the LS means along with the difference between the LS means (fordadistrogene movaparvovec minus placebo) and the corresponding standard error, two-sided p-value, and 95% CI will be provided for change from baseline for all visits through Week 52 where PODCI is assessed.

Graphical displays:

- The fordadistrogene movaparvovec and placebo LS means, and 95% CIs for the LS means for each visit will be displayed graphically.

6.2.5.2. Meaningful Within-Patient Change Threshold

eCDF curves of change from Baseline at Week 52 in the Modified PODCI: Transfer and Basic Mobility Core Scale (Pediatric Parent) and of change from Baseline at Week 52 in the Modified PODCI: Sports and Physical Functioning Core Scale (Pediatric Parent) will be provided as described in [Section 5.4](#).

6.3. Other Endpoint(s)

None.

6.3.1. Ankle Range of Motion

Endpoint: Change from Baseline at Week 52 in passive ankle range of motion (dorsiflexion).

Analysis:

- Analysis set: FAS ([Section 4](#)).
- Analysis methodology: Not applicable.

- Missing data: All available data in the reporting period will be included. Missing data will not be imputed.
- N, mean, SD, median, Q1, Q3, minimum, and maximum for the observed value and change from baseline will be provided for fordadistrogene movaparvovec and placebo by visit and for left ankle and right ankle separately.

6.3.2. Real-life Function Parameters as Assessed by Actigraphy

Endpoint: Change from Baseline at Week 52 in each of the selected parameters assessed by actigraphy:

- Steps per day (steps);
- 95th percentile of cadence (steps/min);
- Median cadence (steps/min);
- Percent time in high activity (%).

Analysis:

- Analysis set: FAS ([Section 4](#)).
- Analysis methodology: Change from baseline in each of the selected parameters assessed by actigraphy will be analyzed using a MMRM approach ([Section 5.2.1.1](#)) including visits through Week 52 (ie, Weeks 9, 18, 35, 52) with additional fixed effects for Baseline (continuous variable), Screening age covariate (continuous variable), Baseline by visit interaction, and Screening age covariate by visit interaction.
- Missing data: All available data in the reporting period will be included. Missing data will not be imputed.
- N, mean, SD, median, Q1, Q3, minimum, and maximum for the observed value and change from baseline will be provided for fordadistrogene movaparvovec and placebo by visit.
- The fordadistrogene movaparvovec and placebo LS means, standard error of each LS mean, and 95% CIs for the LS means along with the difference between the LS means (fordadistrogene movaparvovec minus placebo) and the corresponding standard error, two-sided p-value, and 95% CI will be provided for change from baseline for all visits through Week 52 where Real-life Function Parameters are assessed.

Graphical displays:

- The fordadistrogene movaparvovec and placebo LS means, and 95% CIs for the LS means at each visit will be displayed graphically.

6.3.3. Loss of Ambulation

Endpoint: Loss of ambulation through Week 52.

Analysis:

- Analysis set: FAS (through Week 52) ([Section 4](#)).
- Analysis methodology: Not applicable.
- Missing data: All available data in the reporting period will be included. Missing data will not be imputed.
- The number (%) of participants with loss of ambulation will be provided for fordadistrogene movaparvovec and placebo. Summary statistics (N, mean, SD, median, Q1, Q3, minimum, and maximum) will be presented for the age of the participant at which loss of ambulation occurs.

6.3.4. Percent Predicted FVC (%pFVC)

Endpoint: Change from Baseline at Week 52 in %pFVC.

- Analysis:
 - Analysis set: FAS ([Section 4](#)).
 - Analysis methodology: Change from baseline will be analyzed using an ANCOVA model ([Section 5.2.1.3](#)) including terms for treatment group, Baseline %pFVC (continuous variable), and Screening age covariate (continuous variable).
 - Missing data: All available data in the reporting period will be included. Missing data will not be imputed.
 - N, mean, SD, median, Q1, Q3, minimum, and maximum at Baseline and Week 52 for the observed value and change from baseline will be provided for fordadistrogene movaparvovec and placebo.
 - The fordadistrogene movaparvovec and placebo LS means, standard error of each LS mean, and 95% CIs for the LS means along with the difference between the LS means (fordadistrogene movaparvovec – placebo) and the corresponding standard error, two-sided p-value, and 95% CI at Week 52 will be provided.

6.3.5. EQ-5D-Y Assessment

Endpoint: Response to each of the 5 dimensions at Week 52 on the EQ-5D-Y proxy assessment at Week 52.

Analysis:

- Analysis set: FAS ([Section 4](#)).
- Analysis methodology: Not applicable.
- Missing data: All available data in the reporting period will be included. Missing data will not be imputed.
- For each of the 5 dimensions, the number and percent of participants responding as ‘no problems’, ‘some problems’, or ‘a lot of problems’ will be provided for fordadistrogene movaparvovec and placebo.
- For each of the 5 dimensions, change from baseline to Week 52 will be summarized using shift tables for fordadistrogene movaparvovec and placebo.

Endpoint: Change from Baseline at Week 52 on the EQ VAS proxy assessment.

Analysis:

- Analysis set: FAS ([Section 4](#)).
- Analysis methodology: Not applicable.
- Missing data: All available data in the reporting period will be included. Missing data will not be imputed.
- N, mean, SD, median, Q1, Q3, minimum, and maximum for the observed value and change from baseline will be provided for fordadistrogene movaparvovec and placebo.

6.3.6. QoL of Caregivers of Participants

If a participant changes his caregiver during the reporting period, from the one at baseline, all values collected after the change will be set to missing.

Endpoint:

- Response to each of the 5 dimensions of the EQ-5D-5L assessment at Week 52 (caregivers of participants).

Analysis:

- Analysis set: Caregivers of participants in the FAS (Section 4). Caregivers of siblings will be included in the analyses only once.
- Analysis methodology: Not applicable
- Missing data: All available data in the reporting period will be included. Missing data will not be imputed.
- For each of the 5 dimensions, the number and percent of caregivers of participants responding as ‘no problems’, ‘slight problems’, ‘moderate problems’, ‘severe problems’, or ‘unable to/extreme problems’ will be provided at Baseline and Week 52 for fordadistrogene movaparvovec and placebo.
- For each of the 5 dimensions, change in response from baseline at Week 52 will be summarized using shift tables for fordadistrogene movaparvovec and placebo.

Endpoints:

- Change from baseline at Week 52 in the EQ-5D-5L VAS assessment (caregivers of participants)
- Change from baseline at Week 52 in the EQ-5D-5L index score (caregivers of participants)

Analysis:

- Analysis set: Caregivers of participants in the All Randomized (Section 4). Caregivers of siblings will be included in the analyses only once.
- Analysis methodology: Not applicable
- Missing data: All available data in the reporting period will be included. Missing data will not be imputed.
- For each participant’s caregiver at baseline, N, mean, SD, median, Q1, Q3, minimum, and maximum at baseline and at Week 52 for observed values and changes from baseline will be provided for fordadistrogene movaparvovec and placebo.
- If more than 5 participants change their caregivers from the ones at baseline during the reporting period, N, mean, SD, median, Q1, Q3, minimum, and maximum at baseline and all visits through Week 78 where EQ-5D-5L is assessed for caregivers for observed values will be provided for fordadistrogene movaparvovec and placebo by visit.

